## 10.1 Adverse Events

An AE is defined as any untoward medical occurrence in a subject received a pharmaceutical product (including investigational drug) during the course of a clinical investigation.

Adverse events will be collected from the time of signed informed consent through EOS. If adverse events onset after EOS were reported, the events will not be used for analysis. Adverse events will be classified by SOC and PT using MedDRA Version 18.1 or higher.

Adverse events that started on or after the first dose of the study drug and up to “End of Study” are defined as treatment-emergent.

Unless otherwise noted, the summary of AEs will be performed for events of treatment-emergent. An overview of AEs will be provided that summarizes subject incidence and the number of AEs, treatment-related AEs, serious adverse events (SAEs), treatment-related SAEs, death due to AEs, AEs leading to discontinuation of study drug, and treatment-related AEs leading to discontinuation of study drug.

The number and percentage of subjects with AEs will be summarized for each treatment group by SOC and PT. Subjects with more than 1 AE in the same SOC will be counted once for the SOC. Similarly, subjects with more than 1 AE in the same PT will be counted once for the PT. Treatment-related AEs, SAEs, treatment-related SAEs, AEs leading to discontinuation of study drug, and treatment-related AEs leading to discontinuation of study drug, death due to AEs will be summarized in the same manner.

Summaries will be provided by maximum severity for the number and percentage of subjects with AEs by SOC and PT. For the summary of AEs by maximum severity, missing severity will be assumed as “severe.” For these summaries, subjects with multiple AEs will be counted only once by the maximum severity within an SOC and PT.

All AEs including AEs not considered treatment-emergent, which have occurred before or after the first dose of the study drug, will be listed by subject.

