### 7.12.2 Timing

AEs will be collected from the time of having signed informed consent through 28 days after the last dose of the study treatment for randomized patients. If a patient withdraws early from the study, the investigator or sub-investigator will make an effort to collect AEs for 28 days after the last dose of the study treatment. Any ongoing AE 28 days after the last dose of study treatment will be followed until resolution, stabilization, the condition becomes chronic, or the patient is lost to follow-up.

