## **8.5 End of Study (EOS [EOT + 28 days])**

- Limited physical examination relevant to the patient's current condition
- Vital signs (including blood pressure, body temperature, pulse rate, and respiratory rate)
- Clinical laboratory tests (hematology, blood chemistry, and urinalysis; see Table 7-1) if required to follow abnormal safety test results
- AE assessment
- Concomitant therapy
- Hospitalization
- Vital status (survival or death)

EOS assessments may be performed by phone to document current patient status, in which case, the physical examination, vital signs, and laboratory tests will not be performed. Any AEs ongoing at EOS (28 days after the last dose of study treatment) will be followed as specified in Section 7.12.2. Continuing laboratory changes that are considered significant and symptoms related to AEs should be followed until resolution, AEs are judged by the investigator to have stabilized, or the patient is lost to follow-up. Pregnancies should be followed as specified in Section 7.12.9.

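### SAP 10.1 cuts the AE summaries off at an undefined EOS date; read as the visit date, an early visit removes up to 3 days of the protocol's 28-day AE window

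*SAP*

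**What the plan says.** **Protocol.** Section 7.12.2 sets the window by time since the last dose: in randomized patients, AEs are "collected from the time of having signed informed consent through 28 days after the last dose of the study treatment". For a patient who leaves early, "the investigator or sub-investigator will make an effort to collect AEs for 28 days after the last dose of the study treatment". Section 7.12.10 treats any AE reported after the initial dose as treatment-emergent and sets no end date; section 9.10.1 uses that definition for the safety analyses. Table 7-2 and Appendix 1 allow the EOS visit at EOT + 28 days, plus or minus 3. EOT is the last day of study treatment.

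**SAP.** Section 10.1 ends the window at EOS: "Adverse events will be collected from the time of signed informed consent through EOS". It then states the exclusion, "If adverse events onset after EOS were reported, the events will not be used for analysis", and caps the definition: "Adverse events that started on or after the first dose of the study drug and up to “End of Study” are defined as treatment-emergent". The same section lists all AEs by subject, including those that are not treatment-emergent. Figure 4-1 and Appendix 1 show EOS with the same 3-day tolerance. Table 6-1, which defines the analysis windows, has no EOS row. Section 15, on changes from the protocol, does not mention an upper limit for TEAEs.

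**The concern.** The protocol counts days from the last dose, whereas the SAP stops at a visit that may be held before those days are complete. An SAE that starts two days after an early EOS visit could be one the site must still report under the protocol, yet the SAP would leave it out of every AE summary. The observation window would also vary between patients according to when the last visit, which may be a telephone call, was booked.

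Early withdrawals raise a second question. The protocol asks sites to keep collecting AEs for these patients, but neither document gives them an EOS date for the analysis. If a programmer used the withdrawal or last-contact date, the events collected at the protocol's request would be excluded.

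The outputs concerned are the TEAE, SAE and fatal-AE summaries. Efficacy analyses do not depend on this rule.

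**Working it through.** **Inputs**
- Protocol AE window: 28 days after the last dose (Protocol 7.12.2).
- EOS visit: EOT + 28, tolerance 3 days either way (Protocol Table 7-2; SAP Figure 4-1). Earliest 28 − 3 = 25; latest 28 + 3 = 31.
- Treatment length: 7 to 14 days expected, up to 21 allowed (Protocol 5.2).
- Arm sizes: about 150 randomized 2:1, so about 100 and 50 (SAP 4.3).

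**Step 1. Days lost or added if EOS is the visit date.** For a visit at EOT + e, protocol days lost = max(0, 28 − e) and days beyond the protocol window = max(0, e − 28).

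| EOS visit | Protocol days lost | Extra days counted |
|---|---|---|
| EOT + 25 | 3 (days 26 to 28) | 0 |
| EOT + 28 | 0 | 0 |
| EOT + 31 | 0 | 3 |

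If EOS is nominal day 28, no protocol day is lost for any visit date.

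**Step 2. Share of the window.** Of the post-treatment days alone, 3/28 = 10.7%. The TEAE summaries count from first dose, so the better denominator is treatment days plus 28:
- 7 days of treatment: 3/35 = 8.6%
- 14 days: 3/42 = 7.1%
- 21 days: 3/49 = 6.1%

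**Step 3. Illustrative counts.** The documents give no AE rate by day. Assume a constant hazard, a 28-day post-treatment risk p of a first event, and the worst case of every EOS visit at EOT + 25. The chance of onset on days 26 to 28 is (1 − p)^(25/28) − (1 − p).

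| Assumed p | Chance | Per 100 (cefiderocol) | Per 50 (BAT) |
|---|---|---|---|
| 5% | 0.0052 | 0.5 | 0.3 |
| 10% | 0.0102 | 1.0 | 0.5 |
| 20% | 0.0194 | 1.9 | 1.0 |
| 30% | 0.0273 | 2.7 | 1.4 |

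These are ceilings under the assumption, because most visits will not fall on the first permitted day.

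**Step 4. Which meaning of EOS applies.** The protocol uses both. Section 8.5 equates EOS with the nominal day: "Any AEs ongoing at EOS (28 days after the last dose of study treatment) will be followed as specified in Section 7.12.2". Section 7.12.9 does the same. The visit schedules in both documents give a range of dates. SAP 9.4.1.6 takes vital status at EOS and censors survivors there, which fits a visit more naturally. The SAP never chooses between the two.

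**Step 5. Effect of the fix.** With the cut-off at the later of day 28 and the EOS visit, days lost = max(0, 28 − max(28, e)) = 0 for every e. A visit at EOT + 31 still contributes 3 extra days.

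**The case against.** The strongest reply is that there may be no conflict. The protocol treats EOS and 28 days after the last dose as the same point, and it describes AE assessment as running through to EOS (Synopsis, Safety Assessments; section 8.1). On that reading the SAP follows the protocol's collection period and loses nothing. This stands as far as it goes: a reader might infer from SAP 10.1 that in-window events are certain to be dropped, and the documents do not support that. They leave the cut-off undefined. The reply does not cover the TEAE cap, which is absent from Protocol 7.12.10 on either reading.

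Three further inferences also go too far.
- *That late events and deaths vanish.* All AEs are listed by subject. The rule works on onset, so a fatal AE that begins before EOS stays in the tables whenever death occurs. SAP 9.4.1.6 adds an ITT mortality analysis that includes deaths after EOS.
- *That early withdrawals lose most of their 28 days.* No section sets EOS at the withdrawal date, and Protocol 7.13 asks for follow-up through EOS where possible. The loss is possible only because the date is unspecified.
- *That the arms are treated unequally.* The same visit tolerance applies to both, and nothing in the documents suggests that visit timing differs by arm.

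Finally, EOS is the last scheduled contact, so few events on days 26 to 28 may be captured after an early visit. That limits the size of the problem. It is no reason to exclude the in-window events that are reported.

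**Conclusion.** The point holds as an undefined cut-off attached to an explicit exclusion rule. For a patient who completes follow-up, the loss is at most 3 days and needs two conditions: EOS programmed as the visit date, and a visit before EOT + 28. On the assumed risks above, the worst case is about 0.5 to 2.7 subjects per 100 and 0.3 to 1.4 per 50. For early withdrawals the size cannot be stated, because it depends on a date that neither document gives.

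The effect on the safety conclusions is likely to be small, and no bias between arms is shown. It is still worth correcting. The rule can remove SAEs that fall inside the protocol's own window from the summaries, and the TEAE cap is an unrecorded departure, although Protocol 9.1 requires departures from its planned analyses to be detailed and justified in the SAP.

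**What to change.** In SAP 10.1, replace the TEAE definition and the exclusion sentence with wording to this effect: treatment-emergent AEs are those with onset from the first dose of study treatment through 28 days after the last dose, or through the EOS visit if that is later, regardless of an early EOS visit or of withdrawal; AEs with later onset are listed only. Writing study treatment rather than study drug makes clear that BAT is included, since the protocol glossary reserves the latter term for S-649266.

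Add a line to SAP 15 recording that the TEAE period now has an upper limit which Protocol 7.12.10 lacks.

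The cost is a few lines of text and one date condition in the programs, with no change to data collection or patient care. Event counts may rise slightly. Patients with a late EOS visit keep up to 3 extra days, so the window is not identical for everyone, but none is shorter than the protocol's 28 days. The change does not create AE ascertainment after an early last visit; it only ensures that in-window events which are reported are counted.

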### 10.1.1 Analysis of Adverse Events Changing Treatment Group for a Subject Who Received Cefiderocol after BAT Administration

As this is an open-label study, it has been observed that one subject received cefiderocol after completion of the randomization assigned study drug regimen of BAT. Therefore, an limited set of key safety analyses which consider this subject as assigned to the cefiderocol arm will be performed for an overview of AEs. These analyses are: the number and percentage of subjects with AEs, SAEs and death due to AEs by SOC and PT.

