## 6.2.4 Rescue Therapy

There is no identified rescue treatment regimen. No addition or substitution of any antibiotic after randomization is allowed unless the patient is assessed as a microbiologic or clinical failure in which case an EOT assessment should occur. If a patient needs to be treated for longer than 21 days, an EOT visit should be performed as soon as possible after last dose (same calendar day) and the patient should be discontinued from the study treatment: 1) in the case of S-649266 (and the adjunctive antibiotic), treatment should

follow local clinical practice; 2) in the case of BAT, it should be continued or changed per local clinical practice. All antibiotics will continue to be recorded in the eCRF until the completion of the EOS assessment.

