### **5.5 Safety Population**

The Safety population includes all randomized subjects who receive at least 1 actual dose of the study treatment (ITT population). The population will be analyzed according to the treatment that the subjects actually received study drug regimen, rather than the treatment to which the subjects were randomized.

Note that, as this is an open-label study, it has been observed that one subject received cefiderocol after completing the randomization assigned study treatment of BAT,. This subject will be included in the Safety Population as having received BAT. However, a limited number of key safety analyses will be repeated with this subject assigned to the cefiderocol arm. (see [section 10.1.1](#) for details).

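### The repeat safety analysis in SAP 10.1.1 moves the one subject who took cefiderocol after BAT as a whole, so any event that began on BAT would be reported under cefiderocol

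*SAP*

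**What the plan says.** SAP 5.5 analyses the Safety population by treatment actually received and then deals with one known case. For the main tables, "This subject will be included in the Safety Population as having received BAT". It adds that "a limited number of key safety analyses will be repeated with this subject assigned to the cefiderocol arm".

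SAP 10.1.1 describes the same case: "it has been observed that one subject received cefiderocol after completion of the randomization assigned study drug regimen of BAT". It states that "key safety analyses which consider this subject as assigned to the cefiderocol arm will be performed for an overview of AEs", and it limits the repeat to "the number and percentage of subjects with AEs, SAEs and death due to AEs by SOC and PT".

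SAP 10.1 sets the window for all of these tables. Treatment-emergent events are "Adverse events that started on or after the first dose of the study drug and up to" EOS, and onsets after EOS are not analysed. A subject counts once per system organ class and once per preferred term. Protocol 7.12.10 starts the window at the first dose of the randomised study or control treatment, which for this subject is the first BAT dose.

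None of these sections divides this subject's events at the first cefiderocol dose.

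**The concern.** The subject had two exposures in sequence, but each analysis gives the subject a single arm for the whole window. The two analyses err in opposite directions. The main analysis can leave an event that began after cefiderocol under BAT. The repeat can report an event that began on BAT alone as a cefiderocol event.

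The second matters more, because the repeat exists to show what happened in people exposed to cefiderocol, and the safety of cefiderocol is the first-listed secondary objective. It covers serious events and fatal events, where a row may hold only one subject. A death or serious event that began before any cefiderocol would then appear in the cefiderocol column with nothing in the table to say so.

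**Working it through.** **Inputs.** About 150 subjects randomised 2:1, about 100 of them treated with cefiderocol (SAP 4.3). One crossover subject, randomised to BAT (SAP 5.5, 10.1.1). These are planned sizes, not actual ones.

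**Plan's figure.** 150 × 2/3 = 100 for cefiderocol, which agrees with SAP 4.3. That leaves 150 × 1/3 = 50 for BAT, including the crossover subject.

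**Denominators.** Main analysis: BAT 50, cefiderocol 100. Repeat as written: BAT 49, cefiderocol 101. Repeat divided at the first cefiderocol dose, with the subject in both arms: BAT 50, cefiderocol 101.

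**A preferred term reported only by this subject:**

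| Onset | Main: BAT, cefiderocol | Repeat as written: BAT, cefiderocol | Divided by onset: BAT, cefiderocol |
|---|---|---|---|
| On BAT only | 1/50 = 2.0%, 0/100 | 0/49, 1/101 = 0.99% | 1/50 = 2.0%, 0/101 |
| After cefiderocol only, before EOS | 1/50 = 2.0%, 0/100 | 0/49, 1/101 = 0.99% | 0/50, 1/101 = 0.99% |
| Both periods | 1/50 = 2.0%, 0/100 | 0/49, 1/101 = 0.99% | 1/50 = 2.0%, 1/101 = 0.99% |

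The two planned columns read the same in all three rows, so the tables cannot tell the cases apart. In the first row the main analysis has the right arm and the repeat the wrong one. In the second row it is the reverse. In the third row neither is right.

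**Largest possible effect.** Suppose x of the other 49 BAT subjects and y of the 100 cefiderocol subjects have the event, and so does this subject. The move from main to repeat changes BAT by (x + 1)/50 − x/49 = (49 − x)/2450, at most 49/2450 = 2.0 points. It changes cefiderocol by (y + 1)/101 − y/100 = (100 − y)/10100, at most 100/10100 = 0.99 point.

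**Commoner events.** At an assumed 5% in everyone else, BAT is (2.45 + 1)/50 = 6.90% in the main analysis against 5.00% in the repeat. Cefiderocol is 5.00% against (5 + 1)/101 = 5.94%. At an assumed 20%, BAT is (9.8 + 1)/50 = 21.60% against 20.00%, and cefiderocol is 20.00% against (20 + 1)/101 = 20.79%. The shift shrinks as the event becomes common, so rare serious or fatal rows are affected most.

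**The case against.** The SAP discloses the case and shows it both ways. Tables count subjects, so placing the whole subject under cefiderocol captures every in-window event that cefiderocol could have caused. That gives the highest possible cefiderocol count in each row, which is a cautious bound for a question about cefiderocol safety. By-subject listings are also planned, so onset can be checked by hand.

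Most of this stands. It would be too strong to infer that neither analysis ever places an event correctly, or that the repeat shows nothing. One of the two is right unless events fall in both periods, and the repeat does work as an upper bound on the cefiderocol count. But the SAP does not label it as a bound. The repeat also takes the subject's BAT-period events out of the BAT column, and no planned summary shows which events followed cefiderocol. The related-event tables do not help here, because SAP 10.1.1 leaves them out of the repeat.

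A literal reading might seem to remove the problem. The protocol glossary reserves the term study drug for cefiderocol, so "Adverse events that started on or after the first dose of the study drug" could be taken to start this subject's window at the first cefiderocol dose. Applied generally, that would leave the BAT arm with no treatment-emergent events and contradict Protocol 7.12.10. SAP 10.1.1 itself uses the term for BAT.

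A reader might also infer that the same fault runs through both arms, because patients who stop for failure move to other antibiotics and are still followed to EOS. The documents do not support a finding on that. Protocol 6.2.4 does say that "in the case of BAT, it should be continued or changed per local clinical practice", but those words concern patients needing more than 21 days of treatment, and they allow BAT to continue. Neither document says how long patients spend on a later regimen. Follow-up to 28 days after the last dose and retention of discontinued patients are deliberate (Protocol 7.12.2, 7.13). Relatedness is judged against study treatment (Protocol 7.12.4), so the related-event tables in SAP 10.1 already partly separate the effects of later drugs. A cut-off at a change of Gram-negative regimen would depend on outcome in an open-label trial. It would also be hard to define where BAT may be de-escalated (Protocol 5.2.2) and additional antibiotics may need adjudication (SAP 6.8).

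**Conclusion.** The point holds for this one subject and is minor. As written, the repeat would report any event that began on BAT before cefiderocol as a cefiderocol adverse event, serious event or death. The main analysis would keep any event that began after cefiderocol and before EOS under BAT. Each row is affected by at most one subject, about 1 point of cefiderocol and 2 points of BAT.

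The size assumes the planned 100 and 50. The direction assumes that the treatment-emergent window starts at the first dose of assigned treatment. The documents do not say when cefiderocol was first given, whether that was before EOS, or whether this subject had any event. If cefiderocol began after EOS, no event that followed it enters either analysis, and only the misplacement of BAT-period events in the repeat remains.

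**What to change.** Keep the main analysis in SAP 5.5 unchanged. In SAP 10.1.1, state that in the repeat this subject's events are divided at the first cefiderocol dose. Onsets from the first BAT dose up to that point count under BAT, and onsets on or after it, up to EOS, count under cefiderocol. Include the subject in both denominators of the repeat and explain this in a footnote.

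The data should already exist. Adverse event onset dates are recorded (Protocol 7.12.1), antibiotics are recorded to EOS (Protocol 6.2.4), and cefiderocol taken as a concomitant drug is reported under its own name (SAP 8.4).

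The cost is a sentence or two in the SAP and a change to the program for the repeat. No further table is needed. The downside is that one subject appears in both denominators of a supplementary table, so planned totals become 50 + 101 = 151 for 150 subjects. Where the subject has no event after cefiderocol, the cefiderocol rate is slightly diluted: 20/100 = 20.0% becomes 20/101 = 19.8%.

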## 10.2 Clinical Laboratory Evaluations

Summary statistics for laboratory test data (hematology and serum chemistry parameters, and other specialized tests) will be presented for each scheduled time point measured

after randomization and for the change from baseline to each time point. If a site reports a laboratory value including sign for numeric value (i.e. “<”, “>”), the value removing sign will be used for analysis.

The number and percentage of subjects with the following prespecified outlier category (Table 10-1) during the postdosing period including unscheduled will be presented by treatment group.

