**Safety Assessments:**

Patient safety will be assessed daily from the time of informed consent, while the patient is hospitalized, and through to EOS by the identification of adverse events (AEs). Adverse events defined as new or worsening symptoms since the time of Randomization will be used to determine the safety of the study treatment. In case treatment duration is extended beyond 14 days, additional safety assessments will be conducted on Day 14. Safety surveillance will extend to up to 28 days after the last dose of the study drug. Clinical laboratory tests of blood chemistry, hematology, and urinalysis will be performed at Screening, EA, EOT, TOC, and FUP. In addition, an electrocardiograph (ECG) will be performed at Screening/baseline. Vital signs including body temperature and AEs will be recorded daily.

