Since S-649266 is mainly eliminated unchanged in urine, patients with reduced renal function (estimated glomerular filtration rate [eGFR]  $< 60$  mL/min/1.73 m^2) determined by modification of diet in renal disease (MDRD) equation, will have their dose reduced based on the degree of renal impairment (Table 5-2). Patients on various forms of hemodialysis, except peritoneal dialysis, are also eligible for the study and dosage will be adjusted as described in Section 5.2. Patients with augmented renal clearance (ARC) determined by eGFR  $\geq 90$  mL/min/1.73 m^2 and creatinine clearance (CrCl)  $\geq 120$  mL/min calculated by the Cockcroft-Gault equation will have their dosing interval shortened (Table 5-2). Dose adjustment should be done both after study required renal function tests as well as those conducted per the best local clinical practice.

Dose adjustment for patients randomized to BAT with reduced renal function will be made according to each drug's country specific label based on the degree of renal impairment.

Sequential oral antibiotic (step-down) therapy is not permitted by this protocol. De-escalation (withdrawal of unneeded antibiotics after consideration of the bacterial culture and susceptibility results) will be assessed no later than Early Assessment (EA).

A patient’s clinical status will be reviewed daily and will be formally evaluated at specified intervals for clinical assessment and safety during hospitalization and periodically during follow-up for approximately 28 days from EOT, ie, End of Study (EOS). End of trial for this study is defined as the last visit of the last patient and is 28 days ( $\pm 3$  days) after the end of treatment for that patient.

The study design is shown in Figure 3-1. The study time and events table is shown in Appendix 1.

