### **9.13 Pharmacoeconomics Associated with Treatment**

The pharmacoeconomics of treatment will focus primarily on the resource utilization required for the treatment of the study qualifying infection. Facility utilization will be assessed by determination of the time in 24-hour days associated with the treatment of the infection:

- Length of Stay (LOS) attributable to the infection
- Days in ICU
- Hours on assisted mechanical ventilation
- Days in isolation for infection control (ICU or ward)
- Discharge status, eg, to home, hospice, or general ward
- Monitoring for renal toxicity or renal replacement therapy utilization

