For the other efficacy and safety endpoints, baseline is defined as the last measurement obtained prior to receipt of the first infusion of study drug.

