**Table 10-1 Outlier for Each Parameter in Laboratory Test**

Parameter (Unit)	Outlier Category
Hemoglobin (g/dL)	Decrease from baseline $\geq 1.5$ g/dL
Platelet count ( $10^3/\mu\text{L}$ )	Decrease from baseline $\geq 25\%$ and value $<$ LLN
	Increase from baseline $\geq 100\%$ and value $>$ ULN
White blood cell count ( $10^3/\mu\text{L}$ )	Decrease from baseline $\geq 50\%$ and value $<$ LLN
	Increase from baseline $\geq 20\%$ and value $>$ ULN
ALT (U/L)	Value $> 3 \times$ ULN
	Value $> 5 \times$ ULN
	Value $> 10 \times$ ULN
	Value $> 20 \times$ ULN
AST (U/L)	Value $> 3 \times$ ULN
	Value $> 5 \times$ ULN
	Value $> 10 \times$ ULN
	Value $> 20 \times$ ULN
AST (U/L) or ALT (U/L)	Value $> 3 \times$ ULN
	Value $> 5 \times$ ULN
	Value $> 10 \times$ ULN
	Value $> 20 \times$ ULN
Total bilirubin (mg/dL)	Value $> 2 \times$ ULN
	Increase from baseline $\geq 50\%$ and value $>$ ULN
PT-INR	Value $> 1.5$
BUN (mg/dL)	Increase from baseline $\geq 50\%$ and value $>$ ULN
Serum creatinine (mg/dL)	Increase from baseline $\geq 0.3$ mg/dL
ALP (U/L)	Increase from baseline $\geq 50\%$ and value $>$ ULN
AST (U/L) or ALT (U/L) + Total bilirubin (mg/dL) or PT-INR	(AST $> 3 \times$ ULN or ALT $> 3 \times$ ULN) and (Total bilirubin $> 2 \times$ ULN or PT-INR $> 1.5$ )

ALP = alkaline phosphatase; ALT = alanine transaminase; AST = aspartate transaminase; LLN = lower limit of normal; PT-INR = prothrombin time-international normalized ratio; ULN = upper limit of normal

All clinical laboratory summaries other than specialized tests will be based on the local laboratory measurements, and only the data that can be converted into standard units will be included in analysis. Summaries for specialized tests will be based on the central

laboratory measurements. Within the laboratory parameters, PTT will not be analyzed since during the study monitoring, study team found PTT was reported mixed with APTT.

All central clinical laboratory data and local clinical laboratory data will be listed. Values outside the normal ranges will be flagged for the central laboratory measurements.

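### The creatinine outlier row in SAP Table 10-1 does not separate patients already on dialysis, does not count new dialysis, and flags more patients the more often they are tested

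*SAP*

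**What the plan says.** The creatinine category in SAP Table 10-1 is "Increase from baseline $\geq 0.3$ mg/dL". It has no relative limb, no upper-limit-of-normal (ULN) limb and no repeat-value requirement. The BUN row of the same table is built differently: "Increase from baseline $\geq 50\%$ and value $>$ ULN".

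SAP Section 10.2 counts subjects who meet a category "during the postdosing period including unscheduled will be presented by treatment group". The analysis set is defined in SAP Section 5.5: "The Safety population includes all randomized subjects who receive at least 1 actual dose of the study treatment". Outside microbiology, SAP Section 6.5 states that "baseline is defined as the last measurement obtained prior to receipt of the first infusion of study drug". This is one value, with no rule on its timing relative to a dialysis session.

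Protocol Section 3.1 states: "Patients on various forms of hemodialysis, except peritoneal dialysis, are also eligible for the study". Protocol Table 5-2 has dosing rows for intermittent hemodialysis, CVVH, and CVVHD or CVVHDF. Neither document separates these patients in the outlier table.

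The scheduled tests are the same in both arms: "Clinical laboratory tests of blood chemistry, hematology, and urinalysis will be performed at Screening, EA, EOT, TOC, and FUP". Protocol Section 8.2.5 adds a Day 14 test if treatment is extended. Further renal testing follows local practice (Protocol Sections 3.1 and 5.3). Laboratory tests at End of Study are done only to follow up abnormal results (Protocol Section 8.5).

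**The concern.** BAT is categorised in Protocol Section 3.1 as polymyxin-based or not, and Protocol Section 9.13 lists "Monitoring for renal toxicity or renal replacement therapy utilization" as an item of interest. The SAP has no pharmacoeconomics section that picks this item up. The creatinine row is the only place in Table 10-1 where a reader can compare the proportion of patients with a creatinine rise by arm.

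Three features weaken that comparison.

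- **Patients already on dialysis.** Under intermittent hemodialysis, creatinine moves with the session. A small absolute threshold against one untimed baseline can be crossed with no change in the kidney.
- **New dialysis.** Dialysis lowers creatinine, so a patient who starts it after baseline without an earlier recorded rise is missed, although this is an important renal event.
- **Number of tests.** The row counts a patient who crosses the threshold at any time. More tests can only raise that proportion. In an open-label trial with testing left to local practice, the number of tests may differ by arm.

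**Working it through.** **The plan's own figure.** The plan gives no expected rate for this table. Its only sizing figure is about 100 treated with cefiderocol, and 150 × 2/3 = 100 reproduces it, leaving about 50 on BAT. One BAT patient is therefore 1/50 = 2 percentage points.

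**Inputs from the documents:** threshold 0.3 mg/dL; 4 scheduled post-baseline chemistry tests (EA, EOT, TOC, FUP).

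**Assumptions, not in the documents:** dialysis swing 0.5 to 3 mg/dL; within-patient CV 5% to 10%; 14 values as a heavily tested case; dialysis share at entry 5% to 10%.

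**1. What 0.3 mg/dL means at different baselines.** 0.3/1.0 = 30%; 0.3/3.0 = 10%; 0.3/5.0 = 6%. The bar falls as baseline rises.

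**2. Intermittent hemodialysis, no true change.** Let the baseline and k later values be independent and uniform over a swing S, with a = 0.3/S. Then

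P(flag) = (1 − a) − (1 − a^(k+1))/(k + 1).

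| Swing S (mg/dL) | a | k = 4 | k = 14 |
|---|---|---|---|
| 0.5 | 0.60 | 21.6% | 33.3% |
| 1 | 0.30 | 50.0% | 63.3% |
| 2 | 0.15 | 65.0% | 78.3% |
| 3 | 0.10 | 70.0% | 83.3% |

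If 5% to 10% of 150 are on dialysis (7.5 to 15 patients) and all are on intermittent hemodialysis, 4 tests flag between 7.5 × 0.216 = 1.6 and 15 × 0.70 = 10.5 of them by timing alone.

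**3. Stable patients not on dialysis, no true change.** Let the baseline and k later values be independent normal with mean m and SD = CV × m. With Z standard normal,

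P(flag) = 1 − E[Φ(Z + 0.3/(CV × m))^k].

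| Baseline m (mg/dL) | CV | k = 4 | k = 14 |
|---|---|---|---|
| 0.8 | 7% | 0.03% | 0.1% |
| 1.0 | 5% | 0.0% | 0.0% |
| 1.0 | 7% | 0.45% | 1.3% |
| 1.0 | 10% | 5.5% | 12.9% |
| 1.5 | 5% | 0.8% | 2.4% |
| 1.5 | 7% | 6.8% | 15.6% |
| 1.5 | 10% | 21.2% | 39.4% |
| 2.0 | 7% | 18.0% | 34.7% |

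Simulation of 200,000 patients agrees at the precision used here.

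**4. Both effects together.** Take 5% on dialysis with a 2 mg/dL swing, CV 7%, and one arm tested 4 times against another tested 14 times:

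- Baseline 1.0: 0.95 × 0.45 + 0.05 × 65.0 = 3.7%, against 0.95 × 1.3 + 0.05 × 78.3 = 5.2%.
- Baseline 1.5: 0.95 × 6.8 + 3.25 = 9.7%, against 0.95 × 15.6 + 3.9 = 18.7%.

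The spurious gap is about 1.5 points in the first case and 9 points in the second, with no renal difference between arms.

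**5. BUN.** In the model of step 3 with CV 7%, fewer than 0.05% meet even the 50% limb, at 4 or 14 values.

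**The case against.** Four replies have force.

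- **The table is descriptive.** SAP Section 6.2 excludes inferential testing apart from one exploratory analysis, and this table does not bear on the primary endpoint. That stands and limits the consequence.
- **Other outputs help.** Section 10.2 also gives creatinine and its change from baseline at each scheduled visit, and the local values are listed. New dialysis can appear as an adverse event, because an abnormal result leading to other therapy counts as clinically significant (Protocol Section 7.12.6), or among concomitant procedures (SAP Section 8.4). These outputs soften the problem. Visit averages are still not a proportion with a rise, and none of them corrects the creatinine row.
- **Counting unscheduled values is a defensible conservative screen.** Between EA and EOT no chemistry is scheduled except the Day 14 test in extended treatment, so a scheduled-only table could miss transient injury. This stands, and it is why the scheduled-only version should be an addition.
- **The testing effect is close to nil at baselines of 1.0 mg/dL or below unless the CV approaches 10%.** Correlation between serial values would also narrow the gain from extra tests. Both points stand. Protocol Table 5-2 does, however, provide for moderate and severe renal impairment and end-stage disease, so raised baselines are expected.

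A reader might also infer three stronger things that the documents do not support. The first is that the table is biased against BAT because polymyxin patients are tested more. Scheduled tests are equal, and cefiderocol dosing itself calls for review of local renal tests. The documents also do not say how completely ad hoc values reach the database. The second is that nearly every dialysis patient is flagged. The calculation gives 22% to 70% over 4 tests, and it covers intermittent hemodialysis only; no timing swing has been shown for continuous therapy. The third is that BUN has the same fault. Its 50% and ULN conditions leave it much less exposed.

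**Conclusion.** The point holds for the creatinine row. As written, the row can count dialysis timing as a renal outlier, can miss new dialysis, and gives a proportion that depends on how often patients are tested. The first and third follow from the wording and arithmetic, and the second from the fact that dialysis lowers creatinine.

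The size rests on assumptions. The calculation gives 22% to 70% of intermittent-hemodialysis patients flagged over 4 tests. In stable patients at CV 7%, moving from 4 to 14 values adds under 1 point at a baseline of 1.0 mg/dL, about 9 points at 1.5 and about 17 at 2.0. The dialysis share, the CV and the number of tests by arm are not in the documents, so the net direction and size of any distortion are unknown. What is affected is the reading of renal safety between arms, not an error rate or the primary result. The change is cheap and worth making before the table is used.

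**What to change.** In SAP Section 10.2 and Table 10-1:

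1. In the creatinine row, leave out patients on RRT at baseline, and show their number and results separately by arm. Doing the same for BUN is optional.
2. Count RRT newly started after the first dose as meeting the creatinine category, or give it its own row by arm. The data are already collected: Protocol Section 6.1 names dialysis among prior procedures, and Section 6.2.2 records procedures after randomization. SAP Section 11 already uses dialysis groups for the PK summaries.
3. Keep the planned all-values table, and add a scheduled-visits-only version of the creatinine row beside it.

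The cost is SAP wording, some programming, a slightly smaller denominator in one row and one extra display. No new data collection is needed.
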